# COLUMBIA-SUICIDE SEVERITY RATING SCALE (C-SSRS)

Since Last Visit

Version 1/14/09

*Posner, K.; Brent, D.; Lucas, C.; Gould, M.; Stanley, B.; Brown, G.; Fisher, P.; Zelazny, J.; Burke, A.; Oquendo, M.; Mann, J.*

#### *Disclaimer:*

*This scale is intended to be used by individuals who have received training in its administration. The questions contained in the Columbia-Suicide Severity Rating Scale are suggested probes. Ultimately, the determination of the presence of suicidal ideation or behavior depends on the judgment of the individual administering the scale.*

*Definitions of behavioral suicidal events in this scale are based on those used in The Columbia Suicide History Form, developed by [name] and [name], Conte Center for the Neuroscience of Mental Disorders (CCNMD), New York State Psychiatric Institute, [name]. (Oquendo M. A., Halberstam B. & Mann J. J., Risk factors for suicidal behavior: utility and limitations of research instruments. In M.B. First [Ed.] Standardized Evaluation in Clinical Practice, pp. 103-130, 2003.)*

*For reprints of the C-SSRS contact [name]., New York State Psychiatric Institute, [name]; inquiries and training requirements contact [contact]*

*© 2008 The Research Foundation for Mental Hygiene, Inc.*

Proprietary confidential information © 2019 Boehringer Ingelheim International GmbH or one or more of its affiliated companies

SUICIDAL IDEATION		

Ask questions 1 and 2. If both are negative, proceed to "Suicidal Behavior" section. If the answer to question 2 is "yes", ask questions 3, 4 and 5. If the answer to question 1 and/or 2 is "yes", complete "Intensity of Ideation" section below.
		Since Last Visit

1. Wish to be Dead Subject endorses thoughts about a wish to be dead or not alive anymore, or wish to fall asleep and not wake up. Have you wished you were dead or wished you could go to sleep and not wake up?
		Yes  No 
If yes, describe:		

2. Non-Specific Active Suicidal Thoughts General, non-specific thoughts of wanting to end one's life/commit suicide (e.g., "I've thought about killing myself") without thoughts of ways to kill oneself/associated methods, intent, or plan during the assessment period. Have you actually had any thoughts of killing yourself?
		Yes  No 
If yes, describe:		

3. Active Suicidal Ideation with Any Methods (Not Plan) without Intent to Act Subject endorses thoughts of suicide and has thought of at least one method during the assessment period. This is different than a specific plan with time, place or method details worked out (e.g., thought of method to kill self but not a specific plan). Includes person who would say, "I thought about taking an overdose but I never made a specific plan as to when, where or how I would actually do it...and I would never go through with it." Have you been thinking about how you might do this?
		Yes  No 
If yes, describe:		

4. Active Suicidal Ideation with Some Intent to Act, without Specific Plan Active suicidal thoughts of killing oneself and subject reports having some intent to act on such thoughts, as opposed to "I have the thoughts but I definitely will not do anything about them." Have you had these thoughts and had some intention of acting on them?
		Yes  No 
If yes, describe:		

5. Active Suicidal Ideation with Specific Plan and Intent Thoughts of killing oneself with details of plan fully or partially worked out and subject has some intent to carry it out. Have you started to work out or worked out the details of how to kill yourself? Do you intend to carry out this plan?
		Yes  No 
If yes, describe:		
INTENSITY OF IDEATION		

The following features should be rated with respect to the most severe type of ideation (i.e., 1-5 from above, with 1 being the least severe and 5 being the most severe).
		Most Severe
Most Severe Ideation:	Type # (1-5)	Description of Ideation
Frequency How many times have you had these thoughts?	(1) Less than once a week (2) Once a week (3) 2-5 times in week (4) Daily or almost daily (5) Many times each day	
Duration When you have the thoughts, how long do they last?	(1) Fleeting - few seconds or minutes (4) 4-8 hours/most of day (2) Less than 1 hour/some of the time (5) More than 8 hours/persistent or continuous (3) 1-4 hours/a lot of time	
Controllability Could/can you stop thinking about killing yourself or wanting to die if you want to?	(1) Easily able to control thoughts (4) Can control thoughts with a lot of difficulty (2) Can control thoughts with little difficulty (5) Unable to control thoughts (3) Can control thoughts with some difficulty (0) Does not attempt to control thoughts	
Deterrents Are there things - anyone or anything (e.g., family, religion, pain of death) - that stopped you from wanting to die or acting on thoughts of committing suicide?	(1) Deterrents definitely stopped you from attempting suicide (4) Deterrents most likely did not stop you (2) Deterrents probably stopped you (5) Deterrents definitely did not stop you (3) Uncertain that deterrents stopped you (0) Does not apply	
Reasons for Ideation What sort of reasons did you have for thinking about wanting to die or killing yourself? Was it to end the pain or stop the way you were feeling (in other words you couldn't go on living with this pain or how you were feeling) or was it to get attention, revenge or a reaction from others? Or both?	(1) Completely to get attention, revenge or a reaction from others (4) Mostly to end or stop the pain (you couldn't go on living with the pain or how you were feeling) (2) Mostly to get attention, revenge or a reaction from others (5) Completely to end or stop the pain (you couldn't go on living with the pain or how you were feeling) (3) Equally to get attention, revenge or a reaction from others and to end/stop the pain (0) Does not apply	

Version 1/14/09

Proprietary confidential information © 2019 Boehringer Ingelheim International GmbH or one or more of its affiliated companies

SUICIDAL BEHAVIOR (Check all that apply, so long as these are separate events; must ask about all types)		Since Last Visit

Actual Attempt: A potentially self-injurious act committed with at least some wish to die, as a result of act. Behavior was in part thought of as method to kill oneself. Intent does not have to be 100%. If there is any intent/desire to die associated with the act, then it can be considered an actual suicide attempt. There does not have to be any injury or harm, just the potential for injury or harm. If person pulls trigger while gun is in mouth but gun is broken so no injury results, this is considered an attempt.
 
Inferring Intent: Even if an individual denies intent/wish to die, it may be inferred clinically from the behavior or circumstances. For example, a highly lethal act that is clearly not an accident so no other intent but suicide can be inferred (e.g., gunshot to head, jumping from window of a high floor/story). Also, if someone denies intent to die, but they thought that what they did could be lethal, intent may be inferred.
 
Have you made a suicide attempt?
 
Have you done anything to harm yourself?
 
Have you done anything dangerous where you could have died?
 
What did you do?
 
Did you _____ as a way to end your life?
 
Did you want to die (even a little) when you _____?
 
Were you trying to end your life when you _____?
 
Or did you think it was possible you could have died from _____?
 
Or did you do it purely for other reasons / without ANY intention of killing yourself (like to relieve stress, feel better, get sympathy, or get something else to happen)? (Self-Injurious Behavior without suicidal intent)
 
If yes, describe: _____
		
Yes  No 
 
—
 
Total # of Attempts
 
—
 
Yes  No 
 
—
 
Yes  No 


Has subject engaged in Non-Suicidal Self-Injurious Behavior?
 
Interrupted Attempt: When the person is interrupted (by an outside circumstance) from starting the potentially self-injurious act (if not for that, actual attempt would have occurred).
 
Overdose: Person has pills in hand but is stopped from ingesting. Once they ingest any pills, this becomes an attempt rather than an interrupted attempt.
 
Shooting: Person has gun pointed toward self, gun is taken away by someone else, or is somehow prevented from pulling trigger. Once they pull the trigger, even if the gun fails to fire, it is an attempt. Jumping: Person is poised to jump, is grabbed and taken down from ledge. Hanging: Person has noose around neck but has not yet started to hang - is stopped from doing so.
 
Has there been a time when you started to do something to end your life but someone or something stopped you before you actually did anything?
 
If yes, describe: _____
		
Yes  No 
 
—
 
Total # of interrupted
 
—
 
Yes  No 
 
—
 
Total # of aborted

Aborted Attempt: When person begins to take steps toward making a suicide attempt, but stops themselves before they actually have engaged in any self-destructive behavior. Examples are similar to interrupted attempts, except that the individual stops him/herself, instead of being stopped by something else.
 
Has there been a time when you started to do something to try to end your life but you stopped yourself before you actually did anything?
 
If yes, describe: _____
		
Yes  No 
 
—
 
Total # of aborted

Preparatory Acts or Behavior: Acts or preparation towards imminently making a suicide attempt. This can include anything beyond a verbalization or thought, such as assembling a specific method (e.g., buying pills, purchasing a gun) or preparing for one's death by suicide (e.g., giving things away, writing a suicide note).
 
Have you taken any steps towards making a suicide attempt or preparing to kill yourself (such as collecting pills, getting a gun, giving valuables away or writing a suicide note)?
 
If yes, describe: _____
		
Yes  No 
 
—


Suicidal Behavior: Suicidal behavior was present during the assessment period?
 
Suicide:
		
Yes  No 
 
—
 
Yes  No 
 
—

Answer for Actual Attempts Only
		
Most Lethal Attempt Date:
 
Enter Code
 
—

Actual Lethality/Medical Damage:
 
 
0: No physical damage or very minor physical damage (e.g., surface scratches).
 
1: Minor physical damage (e.g., lethargic speech; first-degree burns; mild bleeding; sprains).
 
2: Moderate physical damage; medical attention needed (e.g., conscious but sleepy, somewhat responsive; second-degree burns; bleeding of major vessel).
 
3: Moderately severe physical damage; medical hospitalization and likely intensive care required (e.g., comatose with reflexes intact; third-degree burns less than 20% of body; extensive blood loss but can recover; major fractures).
 
4: Severe physical damage; medical hospitalization with intensive care required (e.g., comatose without reflexes; third-degree burns over 20% of body; extensive blood loss with unstable vital signs; major damage to a vital area).
 
5: Death
 
 
Potential Lethality: Only Answer if Actual Lethality=0
 
Likely lethality of actual attempt if no medical damage (the following examples, while having no actual medical damage, had potential for very serious lethality: put gun in mouth and pulled the trigger but gun fails to fire so no medical damage; laying on train tracks with oncoming train but pulled away before run over).
 
0 = Behavior not likely to result in injury
 
1 = Behavior likely to result in injury but not likely to cause death
 
2 = Behavior likely to result in death despite available medical care
		
Enter Code
 
—
 
Enter Code
 
—

[figure not shown]
Proprietary confidential information © 2019 Boehringer Ingelheim International GmbH or one or more of its affiliated companies

## 11. DESCRIPTION OF GLOBAL AMENDMENT

This is the original protocol.

### 11.1 GLOBAL AMENDMENT 1

Date of amendment	
EudraCT number	
EU number	
BI Trial number	
BI Investigational Medicinal Product(s)	
Title of protocol	
To be implemented only after approval of the IRB / IEC / Competent Authorities	
To be implemented immediately in order to eliminate hazard – IRB / IEC / Competent Authority to be notified of change with request for approval	
Can be implemented without IRB / IEC / Competent Authority approval as changes involve logistical or administrative aspects only	
Section to be changed	
Description of change	
Rationale for change	

2. LIST OF ABBREVIATIONS

See Medicine Glossary:

website: glossary

Term	Definition / description
ALT	Alanine Aminotransferase
ANCOVA	Analysis of covariance
AST	Aspartate Aminotransferase
AUC _{0-tz}	Area under the concentration-time curve of the analyte in plasma over the time interval from 0 to the last quantifiable data point
AUC _{0-∞}	Area under the concentration-time curve of the analyte in plasma over the time interval from 0 extrapolated to infinity
BMI	Body mass index
BP	Blood pressure
CARE	Clinical Analysis and Reporting Environment
CI	Confidence Interval
C _{max}	Maximum measured concentration of the analyte in plasma
CV	Arithmetic Coefficient of Variation
DB	Dose Proportionality, Between-Subject Design
DILI	Drug induced liver injury
ECGPCS	ECG Pharmacokinetic Concentration Set
gCV	Geometric Coefficient of Variation
gMean	Geometric Mean
HR	Heart rate
IQRMP	Integrated Quality and Risk Management Plan
LLT	Lower Level Term
Max	Maximum
MedDRA	Medical Dictionary For Regulatory Activities
Min	Minimum
N	Number non-missing observations
P10	10 th percentile
P90	90 th percentile
PKS	Pharmacokinetic parameter analysis set

Term	Definition / description
PR	Pulse rate
Q1	1 st quartile
Q3	3 rd quartile
QD	Quaque die, once daily
RAGe	Report Appendix Generator system
REP	Residual Effect Period
RR	Respiratory rate
SAS [®]	Statistical Analysis System
SD	Standard Deviation
SOC	System Organ Class
TS	Treated Set
ULN	Upper Limit of Normal
WHO-DD	World Health Organization Drug Dictionary

3. INTRODUCTION

As per ICH E9 ([1](#)), the purpose of this document is to provide a more technical and detailed elaboration of the principal features of the analysis described in the protocol, and to include detailed procedures for executing the statistical analysis of the primary and secondary endpoints and other data.

This trial statistical analysis plan (TSAP) assumes familiarity with the Clinical Trial Protocol (CTP). In particular, the TSAP is based on the planned analysis specification as written in CTP Section 7 “Statistical Methods and Determination of Sample Size”. Therefore, TSAP readers may consult the CTP for more background information on the study, e.g., on study objectives, study design and population, treatments, definition of measurements and variables, planning of sample size, randomisation.

Study data (including data entered in the RAVE EDC system and external data provided by suppliers) will be stored in a Clinical Data Repository (CDR).

Pharmacokinetic (PK) parameters will be calculated using Phoenix WinNonlinTM software (version 6.3 or higher, Certara USA Inc., Princeton, NJ, USA).

The statistical analyses will be performed within the validated working environment CARE, including SAS[®] (current Version 9.4, by SAS Institute Inc., Cary, NC, USA), and a number of SASTM-based tools (e.g., macros for the analyses of adverse event (AE) data or laboratory data; Report Appendix Generator system (RAGe) for compilation/formatting of the CTR appendices).

4. CHANGES IN THE PLANNED ANALYSIS OF THE STUDY

All analyses described in the TSAP are outlined in the CTP. The following changes compared to the protocol will be made:

In the protocol, it is stated that the medical examination at screening will include alcohol history. However, alcohol history is not captured in the eCRF, and thus, will neither be listed nor included in tables.

5. ENDPOINTS

5.1 PRIMARY ENDPOINT

Section 2.1.2 of the CTP:

The primary endpoint for assessment of safety and tolerability of BI 1358894 is the number [N (%)] of subjects with drug related adverse events.

5.2 SECONDARY ENDPOINTS

5.2.1 Key secondary endpoints

This section is not applicable as no key secondary endpoints have been defined in the CTP.

5.2.2 Secondary endpoints

Section 2.1.3 of the CTP:

The following pharmacokinetic parameters will be determined for BI 1358894 if feasible:

- *AUC_{0-t_z} (area under the concentration-time curve of the analyte in plasma over the time interval from 0 to the last quantifiable data time point t_z)*
- *AUC_{0-∞} (area under the concentration-time curve of the analyte in plasma over the time interval from 0 extrapolated to infinity)*
- *C_{max} (maximum measured concentration of the analyte in plasma)*

6. GENERAL ANALYSIS DEFINITIONS

6.1 TREATMENTS

It is planned that in total 24 Japanese healthy male subjects participate in this study, according to 3 sequential dose groups comprising 8 subjects per group. Within each dose group, 6 subjects will receive BI 1358894 and 2 will receive placebo.

For details of dosage and formulation see Table 6.1: 1 below.

Table 6.1: 1 Labels for treatments for use in the CTR

Dose group	Treatment		Short label
1-3	P*	Placebo, tablet, qd	Placebo
1	A	BI 1358894, 2*25 mg tablet, po, qd	BI 50mg
2	B	BI 1358894, 1*100 mg tablet, po, qd	BI 100mg
3	D	BI 1358894, 2*100 mg tablet, po, qd	BI 200mg

‘qd’ means here a single drug administration, not a regular drug administration per day.

*: The placebo group in the safety evaluation will consist of all placebo treated subjects, regardless of the dose group in which they were treated.

The following separate study phases will be defined for the analyses of AEs:

- **Screening** (ranging from 0:00h (midnight) on day of informed consent until administration time of study drug (BI or Placebo))
- **On treatment**
 - **BI/Placebo treatment** (separately for each treatment, ranging from the time of administration of BI 1358894 or Placebo until 0:00h (midnight) on the day after trial termination date)

Please note that all AEs reported between start of trial drug administration and the trial termination date will be considered on treatment (i.e. no follow-up period is considered in this trial).

Two types of AE displays will be provided in the report:

A) Section 15.3 and Appendix 16.1.13.1.8 (for ClinicalTrials.gov) of the CTR displays:

In these displays, the on treatment phase will be analysed (labelled with the name of the study treatment (short label)). Screening will not be included in this analysis.

The following totals will be provided in addition:

- a total over all BI treated phases (“**BI Total**”)

- a total over all on treatment phases included in this analysis ("Total on treatment") (Section 15.3 only)

B) Section 15.4 and Appendix 16.1.13.1.8 (except for ClinicalTrials.gov) of the CTR displays:

- Screening
- On treatment (labelled with the name of the study treatment (short label))

In Section 16.1.13.1.8 AE tables, the following totals will be provided in addition:

- a total over all BI treated phases ("BI Total")
- a total over all study phases ("Total")

Tables of vital signs, ECG and laboratory values will present results by the above mentioned on treatment phase.

For detailed information on the handling of the treatments refer to Technical TSAP ADS (analysis data set) plan and Analysis Data Reviewer's guide.

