#### **2.1.2 Primary endpoint**

The primary endpoint for assessment of safety and tolerability of BI 1358894 is the number [N(%)] of subjects with drug related adverse events.

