### 7.3.4 Safety analyses

Safety will be assessed as defined by the endpoints listed in Section [2.1.2](#) and 2.2.2 based on the treated set (TS). Safety analyses will be descriptive in nature and will be based on BI standards.

For all analyses the treatment actually administered (= treatment at onset) to the subject will be used (any deviations from the randomised treatment will be discussed in the minutes of the Report Planning Meeting).

Treatments will be compared in a descriptive way. The placebo group in the safety evaluation will consist of all subjects treated with placebo, regardless of the dose group in which they were treated. The test treatment groups will be compared to the placebo group in a descriptive way. Tabulations of frequencies/proportions will be used for the evaluation of categorical (qualitative) data, and tabulations of descriptive statistics will be used to analyse continuous (quantitative) data.

Measurements (such as ECGs, vital signs, or laboratory parameters) or AEs will be assigned to treatments (see Section [5.2](#)) based on the actual treatment at the planned time of the measurement or on the recorded time of AE onset (concept of treatment-emergent AEs).

Therefore, measurements planned or AEs recorded prior to intake of trial medication will be assigned to the screening period, those between trial medication intake until the trial termination date will be assigned to the treatment period. These assignments including the corresponding time intervals will be defined in detail in the trial statistical analysis plan (TSAP). Note that AEs occurring after the last per protocol contact but entered before database lock will be reported to Pharmacovigilance only and will not be captured in the trial database.

Additionally, further treatment intervals (called analysing treatments) may be defined in the TSAP in order to provide summary statistics for other than above periods, such as combined treatments, on-treatment totals, or periods without treatment effects (such as screening and post-study intervals).

Adverse events will be coded using the Medical Dictionary for Regulatory Activities (MedDRA). Frequency, severity and causal relationship of AEs will be tabulated by

Proprietary confidential information © 2019 Boehringer Ingelheim International GmbH or one or more of its affiliated companies

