	4	72:00**		first of three replicate ECG**
	5	96:00**		first of three replicate ECG**
	6	120:00**		first of three replicate ECG
	7	144:00**		first of three replicate ECG
3	10 to 14* 29 to 33**		End of trial examination	NA

*for dose groups 1 and 2

**for dose group 3

The baseline value of an ECG variable is defined as the mean of the triplicate ECG measurements prior to drug administration.

Section 5.2.4.1 of the CTP: A centralised evaluation (during study or post study) of all 12-lead ECGs recorded on Day 1 to Day 3 (48h) for Dose Groups 1 and 2 or on Day 1 to Day 7

(144h) for Dose Group 3 will be performed by an independent ECG laboratory. This analysis will include the determination of cardiac axis (automatic evaluation based on a validated GE-12-SL-algorithm or equivalent) as well as the intervals RR, PR, QRS and QT measured semi-automatically. With the exception of the first triple ECG (used as baseline before the drug administration), only the first of the three replicate ECGs at a single assessment time will be evaluated. [...].

For the exposure response analyses, pairs of ECG variables and corresponding plasma concentrations will be built using the same planned time points, e.g. HR change from baseline and the plasma concentration measured at planned time 0:30 will build one pair. Whether a time deviation between PK blood sampling time and corresponding ECG recording is too big and the pair has to be excluded from the analysis will be decided no later than at the RPM. This critical time deviation depends on the PK properties. When plasma concentrations are expected to change only little around a given time point, the acceptable time deviation between ECG recording and PK blood sampling may be bigger.

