7. PLANNED ANALYSIS

The placebo group in the safety evaluation will consist of all placebo treated subjects, regardless of the dose group in which they were treated.

Safety analysis (refer to [Section 7.8](#)) will be performed by and will be presented in Sections 15.1 to 15.4 of the CTR and in Appendix 16.2 and 16.1.13.1.

Inferential statistical analyses of PK endpoints (refer to Section [7.5.2](#)) will also be performed by and will be presented in Section 15.5 of the CTR and in Appendix 16.1.13.3.

Descriptive data analysis of PK parameters and concentrations will be performed by . The individual values of all subjects and descriptive statistics will be presented in Appendix 16.1.13.5 and Section 15.6 of the CTR, respectively.

The format of the listings and tables will follow the standards defined in the BI standards with the exception of those generated for PK-calculations [\(6\)](#).

The individual values of all subjects will be listed, sorted by treatment group, subject number, and visit.

The listings except PK evaluations will be included in Appendix 16.2 of the CTR.

For end-of-text tables, the set of summary statistics for non-PK parameters is:

N	number non-missing observations
Mean	arithmetic mean
SD	standard deviation
Min	minimum
Median	median
Max	maximum

For analyte concentrations, the following descriptive statistics will additionally be calculated:

CV	arithmetic coefficient of variation
gMean	geometric mean
gCV	geometric coefficient of variation

For PK parameters, the following descriptive statistics will additionally be calculated:

CV	arithmetic coefficient of variation
gMean	geometric mean
gCV	geometric coefficient of variation
P10	10th percentile
Q1	1st quartile
Q3	3rd quartile
P90	90th percentile

The data format for descriptive statistics of concentrations will be identical with the data format of the respective concentrations. The descriptive statistics of PK parameters will be calculated using the individual values with the number of decimal places as provided by the evaluation program. Then the individual values as well as the descriptive statistics will be reported with three significant digits in the CTR.

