7.8.1 Adverse events

AEs will be coded with the most recent version of MedDRA.

The analyses of AEs will be descriptive in nature and will be based on BI standards.

The standard AE analyses will be based on the number of subjects with AEs (and not on the number of AEs).

For analysis, multiple AE occurrence data on the electronic case report form (eCRF) will be collapsed into an AE provided that all of the following applies:

- All AE attributes are identical (lower level term (LLT), intensity, action taken, therapy required, seriousness, reason for seriousness, relationship, outcome, AE of special interest (AESI))
- The occurrences were time-overlapping or time-adjacent (time-adjacency of two occurrences is given if the second occurrence started within one hour after end of the first occurrence).

Section 5.2.6.1.5 of the CTP: *The AESI for this trial is hepatic injury, as defined by the following alterations of hepatic laboratory parameters:*

- *An elevation of AST (aspartate aminotransferase) and/or ALT (alanine aminotransferase) ≥ 3 -fold ULN combined with an elevation of total bilirubin ≥ 2 -fold ULN measured in the same blood sample, or*
- *Aminotransferase (ALT, and/or AST) elevations ≥ 10 -fold ULN*

These lab findings constitute a hepatic injury alert and the subjects showing these lab abnormalities need to be followed up according to the 'DILI checklist' provided in the ISF. In case of clinical symptoms of hepatic injury (icterus, unexplained encephalopathy, unexplained coagulopathy, right upper quadrant abdominal pain, etc.) without lab results (ALT, AST, total bilirubin) available, the Investigator should make sure that these parameters are analysed, if necessary in an unscheduled blood test. Should the results meet the criteria of hepatic injury alert, the procedures described in the DILI checklist should be followed.

The analysis of adverse events will be based on the concept of treatment emergent AEs.

Section 1.2.6 of the CTP: *The residual effect period (REP) for BI 1358894, the time interval when measureable drug levels or pharmacodynamics (PD) effects are still likely to be present after the last administration, is not known at this early stage of development.*

Section 7.3.4 of the CTP: *Therefore, measurements planned or AEs recorded prior to intake of trial medication will be assigned to the screening period, those between trial medication intake until the trial termination date will be assigned to the treatment period.*

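### Drug-related AEs are counted over 9–13 days at 50 and 100 mg but 28–32 days at 200 mg, so the primary table mixes dose with observation time

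*SAP*

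**What the plan says.** Protocol section 2.1.2 sets the primary endpoint as "the number [N(%)] of subjects with drug related adverse events". SAP section 7.8.1 confirms that AE analyses count subjects rather than events.

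The counting window is the same in both documents. SAP section 6.1: "all AEs reported between start of trial drug administration and the trial termination date will be considered on treatment", with no separate follow-up phase. Protocol section 7.3.4, on AEs after dosing: "those between trial medication intake until the trial termination date will be assigned to the treatment period".

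The end of trial differs by dose group. SAP Table 6.7: 1 gives the days as "10 to 14* 29 to 33". The first range is for Dose Groups 1 and 2, the second for Dose Group 3, and the two protocol flow charts agree.

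Placebo is pooled (SAP section 7): "The placebo group in the safety evaluation will consist of all placebo treated subjects, regardless of the dose group in which they were treated". Protocol section 7.3.4 then says: "The test treatment groups will be compared to the placebo group in a descriptive way". Under SAP section 7, percentages are based on all subjects in the analysis set, with no adjustment for time observed.

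**The concern.** A subject's status on this endpoint can change only from no to yes, so a longer watch can only raise the percentage. The 200 mg group is watched at least twice as long as the lower dose groups, and pooled placebo is a blend of the two schedules. If some AEs judged related begin after about two weeks, the percentage at 200 mg can exceed the others because of the calendar rather than the dose. Placebo would then be too high a reference for 50 and 100 mg and too low a one for 200 mg.

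The planned drug-related AE table is by treatment, system organ class and preferred term, with no dimension for time of onset, so it cannot show whether this has happened. Protocol section 3.2 discusses observer bias and time effects from sequential dosing and still expects unbiased treatment comparisons, but does not mention unequal follow-up. Protocol section 7.3.4 would allow further analysis intervals to be defined, yet SAP section 6.1 defines only screening and on treatment.

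**Working it through.** **Inputs.** Three dose groups, each with 6 active and 2 placebo subjects (protocol section 3.1): 3 × (6 + 2) = 24, which reproduces the stated total. Pooled placebo is 3 × 2 = 6. The plan states no power or event figure to reproduce.

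**Observation time.** Days after dosing = study day − 1. The flow charts follow this rule (192 h is Day 9, 672 h is Day 29). The trial termination date is not defined in the supplied text. It is read here as the subject's end of trial, which agrees with protocol section 5.2.6.2.1.

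| Column | End of trial | Days after dosing | Mid-window | Subject-days at mid-window |
|---|---|---|---|---|
| 50 mg, 100 mg (6 each) | Day 10–14 | 9–13 | 11 | 66 each |
| 200 mg (6) | Day 29–33 | 28–32 | 30 | 180 |
| Pooled placebo (4 short + 2 long) | both | 15.3–19.3 (mean) | (4×11 + 2×30)/6 = 17.3 | 104 |

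Ratio of 200 mg to 50/100 mg: 28/13 = 2.15 to 32/9 = 3.56; at mid-window 30/11 = 2.7.

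**Scheduled AE questioning after dosing**, from the last column of each flow chart:

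- Dose Groups 1–2: 10 marks from 0:30 to 12:00, then 24, 34, 48, 72, 96, 120, 144, 168 and 192 h, giving 19. After 192 h: end of trial only, 1.
- Dose Group 3: the same without 168 h, giving 18. After 192 h: 240, 336, 504 and 672 h and end of trial, 5.

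Ascertainment is nearly equal to 192 h and diverges only afterwards.

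**Possible size, constant rate (upper-type illustration).** Assume no drug effect and a constant rate λ of related AEs per subject-day. Then P = 1 − exp(−λ × days), and placebo = [4·P(11) + 2·P(30)]/6. The values of λ are assumptions.

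| λ per day | 50/100 mg | Pooled placebo | 200 mg |
|---|---|---|---|
| 0.005 | 5.4% | 8.2% | 13.9% |
| 0.01 | 10.4% | 15.6% | 25.9% |
| 0.02 | 19.7% | 28.2% | 45.1% |

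At λ = 0.01 this is 0.6, 0.9 and 1.6 subjects of 6. The chance of at least one affected subject among 6 is 1 − (1 − 0.104)^6 = 48% at 50 or 100 mg, against 1 − (1 − 0.259)^6 = 84% at 200 mg.

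**Possible size, early-loaded hazard.** Fix the short-window proportion at 10%, so h = −ln(0.90). Let f be the assumed share of the total hazard falling after the short window. Then P(200 mg) = 1 − exp(−h/(1 − f)), and placebo = [4 × 10% + 2 × P(200 mg)]/6.

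| f | 50/100 mg | Pooled placebo | 200 mg |
|---|---|---|---|
| 0 | 10.0% | 10.0% | 10.0% |
| 0.10 | 10.0% | 10.3% | 11.0% |
| 0.25 | 10.0% | 11.0% | 13.1% |
| 19/30 = 0.63 (constant rate) | 10.0% | 15.0% | 25.0% |

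**With a common window.** The 192 h visit (Day 9) is on both schedules and precedes the earliest permitted end of trial (Day 10). Counting everyone over those 8 days makes the ratio 1. With no drug effect the expected percentages are then equal in all columns, for example 1 − exp(−0.01 × 8) = 7.7%.

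**The case against.** The strongest reply is that little rests on this table. The trial tests no hypothesis, is not powered, and has 6 subjects per column, so one subject is already 16.7 percentage points. After a single dose, related AEs should come early: protocol section 5.2.6.1.7 tells investigators to weigh time to onset. In the early-loaded cases with f up to 0.25, the distortion at 200 mg is at most 3.1 points, about 0.19 of a subject. That stands, and it makes this a matter of interpretation rather than of error rates. It does not settle where the hazard falls. SAP section 7.8.1 says the residual effect period "is not known at this early stage of development", blood sampling at 200 mg runs to 672 h, and investigators know the dose level.

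Second, individual listings are planned and onset times are recorded, so with 24 subjects a reader could find any late event. This is true, but it is reconstruction after the fact and gives no like-for-like comparison in the primary result. The SAP also refers to an analysis dataset plan and company standards that were not supplied, so the absence of a common window is established only for the supplied text.

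Third, total questioning differs little: 20 occasions against 23, and the 672 h visit may coincide with end of trial. This is also correct. The main difference is calendar time; the imbalance in questioning is confined to the period after 192 h.

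Finally, a comparator of two placebo subjects is thin, since one event is 50%. That display is therefore optional.

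**Conclusion.** The concern holds. Observation is 2.15 to 3.56 times as long at 200 mg as at 50 or 100 mg, and pooled placebo matches no active group. The direction is certain: longer observation can only raise the count. The comparison of 50 with 100 mg is unaffected.

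The size cannot be derived from the documents. It ranges from nothing, if all related AEs begin inside the short window, to about 15 percentage points between 200 mg and the lower doses (25.9 − 10.4 = 15.5) at an assumed constant 0.01 per day. Higher assumed rates give more. These figures assume that all subjects complete, with end of trial at mid-window. No test depends on the table and the protocol states no escalation rule based on it. The change is worth making because this is the primary result, its main dose comparison is confounded with time, and the remedy is cheap.

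**What to change.** Keep the to-termination primary endpoint, so that no late AE leaves the primary result. In SAP sections 6.1 and 7.8.1:

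1. Pre-specify one additional table of subjects with drug-related AEs with onset from dosing to the 192 h visit, by treatment. Name it as the basis for comparing 200 mg with the lower doses and each dose with pooled placebo.
2. In the to-termination table, state the observation days for each column.
3. Optionally, show the two Dose Group 3 placebo subjects beside 200 mg, as they are the only placebo subjects sharing its schedule.

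The cost is SAP wording and one table built from onset times already collected. It needs no protocol change and no new data. The drawback is that AEs starting after 192 h do not enter the common-window comparison. They remain in the primary table, which matters while the residual effect period is unknown.
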